8.3.1.1. Recording of Adverse Events

Adverse events should be collected and recorded for each patient from the date of the first screening/eligibility assessment until the end of their participation in the study, i.e., the patient has discontinued or completed the study.

Reporting of AEs prior to first dose should only include SAEs or AEs resulting from any protocol-related interventions.

Adverse events are to be recorded on the AE page of the eCRF. The following information will be recorded at the time the AE is reported and during follow up during the course of the AE:

- Whether or not the AE is an SAE (see [Section 8.3.1.2.1](#))
- AE severity using CTCAE criteria (see [Section 8.3.1.2.2](#))
- AE relationship to study drug (see [Section 8.3.1.2.3](#))
- Action taken; including but not limited to, none, study drug dose modification or discontinuation, required concomitant medication, required procedure, or other
- Outcome: recorded as event resolved, resolved with sequelae, ongoing, or death

If an adverse event is persistent i.e. continues between various study assessment timepoints without resolution it should be recorded only once (see [Section 8.3.1.3](#)).

8.3.1.2. Assessment of Adverse Events

Each AE will be assessed by the Principal Investigator per the categories discussed in the following sections.

8.3.1.2.1. Serious Adverse Events (SAEs)

The Investigator is responsible for determining whether an AE meets the definition of an SAE. An SAE is any AE that results in any of the following outcomes:

- Death
- Life-threatening, i.e., an AE that, in the investigator's opinion, places the subject at immediate risk of death
- Inpatient hospitalization or prolongation of existing hospitalization
- A persistent or significant disability or incapacity, i.e., a substantial disruption in the subject's ability to conduct normal life functions
- A congenital anomaly or birth defect in a neonate or infant born to a mother exposed to study drug

- Significant medical events that, in the opinion of the Investigator, may jeopardize the subject or may require medical or surgical intervention to prevent any of the outcomes listed in this definition.

8.3.1.2.2. Severity

The severity of an event describes the degree of impact upon the subject and/or the need for medical care necessary to treat the event. All clinical AEs encountered during the clinical study will be reported on the AE page of the eCRF. Severity of AEs will be graded based on a modified CTCAE, Version 5.0 and reported in detail as indicated on the eCRF. For any AEs not found in the CTCAE, a description of intensity grading can be found below:

Grade 1 - Mild	Asymptomatic or mild symptoms; clinical or diagnostic observations only; intervention not indicated.
Grade 2 - Moderate	Minimal, local or noninvasive intervention indicated; limiting age-appropriate instrumental activities of daily living.
Grade 3 - Severe	Medically significant but not immediately life-threatening; hospitalization or prolongation of hospitalization indicated; disabling; limiting self-care activities of daily living.
Grade 4 - Life-threatening	Life threatening consequences; urgent intervention indicated
Grade 5 – Death	Death related to AE

Any change in severity of a persistent AE will be captured by recording a new AE with the current severity and a start date of when the severity changed. The prior event will be updated with a stop date of when the severity changed. When changes in the severity of an AE occur more frequently than once a day, the maximum intensity for the event should be noted for that day.

8.3.1.2.3. Relationship to Study Drug

The Principal Investigator will assess the causality/relationship between the study drug and the AE. One of the categories described in [Table 3](#) should be selected based on medical judgment, considering the definitions below and all contributing factors.

Table 3 Assessment of Relationship of Adverse Events to Study Drug

The Investigator should assess causality by answering either “related” or “unrelated” to the question, “Is there a reasonable possibility that the event may have been caused by the study treatment?”.

Related	A clinical event, including laboratory test abnormality, occurring in a plausible time relationship to treatment administration, and which concurrent disease or other drugs or chemicals cannot explain.
Unrelated	A clinical event, including laboratory test abnormality, with little or no temporal relationship with treatment administration.

The following factors may be used in consideration of causality assessment:

- Temporal relationship of the event onset to initiation of study drug
- Amount and duration of study treatment exposure
- Course of the event, including consideration for challenge/rechallenge:
 - Did the event abate after study treatment was reduced or interrupted? Did the event reappear after study treatment was reintroduced?
- Confounding risk factors in the patient that may explain or are associated with the event
- Concomitant medications known to cause or are associated with the event
- Known association of the event with the disease under study
- Known association of the event with similar study treatments

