8.3.1.2.4. Suspected Unexpected Adverse Reactions (SUSARs)

Suspected unexpected adverse reactions (SUSARs) are SAEs that are unexpected per the Reference Safety Information section of the IB and judged by the Investigator and/or Sponsor to be related to ESK-001.

An adverse reaction is ‘unexpected’ if its nature and severity are not consistent with the information about the study drug:

- In the case of a product with a marketing authorization, in the summary of product characteristics for that product.
- In the case of any other investigational product, in the Investigator’s Brochure relating to the trial in question

The Sponsor or designee will report SUSARs to the appropriate regulatory authorities and Investigator’s as required, according to the local law.

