10.4.1. Adverse Events

Verbatim descriptions of treatment-emergent adverse events will be mapped to thesaurus terms using the Medical Dictionary for Regulatory Activities (MedDRA). Adverse events will be tabulated by body system and preferred term. Summaries of adverse events by severity will be provided. Adverse events judged by the investigator to be related to treatment (ESK-001 or placebo) will be prepared. Serious adverse events will be summarized similarly. Adverse events leading to discontinuation from the study or treatment will be listed and tabulated.

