8.1 Adverse Events

AEs will be coded to MedDRA version 25.0. AEs will be presented by SOC and PT, unless otherwise noted, in order of descending frequency on the overall total, and multiple occurrences of the same event in the same participant will be counted only once in the tables.

The following summaries of AEs will be provided:

- Overall summary of TEAEs
- All TEAEs
- Study drug related TEAE
- TEAEs by severity
- Grade 3 or higher TEAE
- Serious TEAEs (SAEs)
- Study drug-related SAEs
- TEAE leading to treatment discontinuation
- TEAE leading to death

By-subject listings of all AEs, SAEs, TEAEs leading to treatment discontinuation, TEAE leading to death will also be provided.

8.2 12-lead Electrocardiogram

12-lead electrocardiogram (ECG) data will be measured and read by local and central laboratory, and will be summarized for all subjects in the Safety Analysis Population.

8.2.1 *ECG Numeric Variables*

HR, PR, QRS, and Fridericia-corrected QT (QTcF) interval based on central ECG read and changes from baseline will be summarized by treatment group using descriptive statistics. The change from baseline of these ECG parameters at each time point will be listed for each subject.

8.2.2 *Categorical Analysis*

The number and percentage of subjects with maximum treatment-emergent post-dose QTcF values based on central ECG read in the following mutually exclusive categories will be summarized by treatment group: > 450 msec, > 480 msec, > 500 msec, > 520 msec, and > 550 msec. The number and percentage of subjects with maximum post-dose QTcF increase from baseline of > 30 msec and > 60 msec (mutually exclusive) will be summarized by treatment group.

Clinical significance will be summarized by treatment group and overall for the local and central ECG reads separately.

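### Protocol Table 3 asks whether a causal link is reasonably possible but defines 'Related' more strictly, so a well-timed adverse event with another possible cause meets neither definition

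*Protocol*

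**What the plan says.** Protocol Section 8.3.1.2.3 gives the investigator two answers, related or unrelated, to one question: "Is there a reasonable possibility that the event may have been caused by the study treatment". The category "should be selected based on medical judgment, considering the definitions below and all contributing factors".

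Table 3 then defines the two answers. A related event is one "occurring in a plausible time relationship to treatment administration, and which concurrent disease or other drugs or chemicals cannot explain". An unrelated event is one "with little or no temporal relationship with treatment administration". A list of factors to weigh follows, including confounding risk factors and "Concomitant medications known to cause or are associated with the event". The list does not say which answer applies when such a factor is present but does not settle the matter.

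The answer is used in these places:

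- Protocol Section 10.4.1: "Adverse events judged by the investigator to be related to treatment (ESK-001 or placebo) will be prepared".
- SAP Section 8.1: a table titled "Study drug related TEAE" and a matching table of drug-related SAEs.
- Protocol Section 8.3.1.2.4: SUSARs are unexpected SAEs "judged by the Investigator and/or Sponsor to be related to ESK-001". Section 8.3.1.4 sets the reporting condition as a reasonable possibility of causation.
- Protocol Section 8.3.1.4: related SAEs are collected without time limit. Unrelated SAEs are collected during the study and to 30 days after the last dose.

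The SAP has no rule for reclassifying events or for resolving a conflict between the question and the definitions.

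**The concern.** Table 3 sets two thresholds for one flag. The question needs only a reasonable possibility of causation. The 'Related' definition needs plausible timing and, in addition, that concurrent disease, other drugs or chemicals cannot account for the event. The 'Unrelated' definition is not the complement of either one, because it looks at timing alone.

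The uncovered kind of event is foreseeable in this trial. Exclusion criterion 17 (Protocol Section 5.3) admits patients on stable cardiovascular medication. SAP Section 5.2 plans a subgroup by co-morbidities that include diabetes, cardiovascular disease, obesity and hypertension. Protocol Section 2.5 says safety assessments are guided by possible immunomodulatory effects and by events associated with JAK inhibition. A cardiovascular event or laboratory change on treatment in such a patient can have plausible timing and a competing explanation together.

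At stake is whether the related-event tables mean one defined thing. With about 65 sites (Protocol Section 4.1), some investigators may code by the question and others by the definitions.

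**Working it through.** The plan states no related-event rate, so there is no figure to reproduce. The check is a cross-classification of the two definitions by timing and by the presence of another explanation of the named kinds (concurrent disease, other drug, chemical).

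| Timing | Other explanation | 'Related' definition | 'Unrelated' definition | Answer to the question |
|---|---|---|---|---|
| Plausible | None | Met | Not met | Yes |
| Plausible | Present | Not met | Not met | Yes or no, by judgment |
| Little or none | None | Not met | Met | Normally no |
| Little or none | Present | Not met | Met | Normally no |

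**Gap.** The second row meets neither definition, although the form allows only two answers.

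**Direction.** Every event that meets the 'Related' definition (first row) would also get a yes to the question. Some events in the second row would get a yes as well, yet they fail the definition. Events passing the definition are therefore a subset of those passing the question, and replacing the question by the definition can remove related events but cannot add any.

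**Size.** Let *p* be the share of reasonably possible events that have another possible explanation, and *q* the share of those coded unrelated. The share leaving the related tables is *p* × *q*. The documents give neither quantity, and *q* could be 0. With purely assumed values of *p* from 0.20 to 0.60 and *q* from 0.25 to 1.00, the product runs from 0.20 × 0.25 = 0.05 to 0.60 × 1.00 = 0.60. A range that wide, resting on no figure in the plan, is not an estimate.

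**Between arms.** Assessment is blinded (Protocol Section 6.7). If the same share *m* = *p* × *q* is lost in every arm, an observed difference in related-event risk is (1 − *m*) times the difference without loss. Rates fall and absolute differences shrink; ratios do not change. Equal loss is an assumption, though blinding makes it plausible.

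**Outputs.** SAP Section 8.1 lists nine summaries. Two are defined by the flag: related TEAEs and related SAEs. The overall TEAE summary might carry a related row, but the SAP does not say. The other summaries (all TEAEs, severity, Grade 3 or higher, serious, leading to discontinuation, leading to death) do not use it. The secondary safety endpoint is incidence of TEAEs and SAEs, also without the flag.

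**Late SAEs.** The Schedule of Assessments puts the last on-site dose at Week 12, Day 84, and the end-of-study visit at Day 115, each ±3 days. For a completer, 30 days after the last dose is Day 84 + 30 = 114 (range 111 to 117), against a visit at Day 112 to 118. Until then SAEs are collected whatever their cause. After both limits have passed, collection under this protocol depends on the flag.

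**The case against.** The strongest reply is that the operative instruction is the question, and a yes/no question is exhaustive. The definitions are to be considered together with medical judgment and a list of factors; they are not stand-alone gates. Weighing concomitant drugs and confounders would have little purpose if any such factor automatically ruled out 'Related'. This stands to the extent that an investigator can properly answer 'related' for an event in the gap. It does not remove the conflict, because the same sentence directs attention to definitions that set a different threshold.

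A second reply concerns direction. A well-timed event fails the 'Unrelated' definition as clearly as it fails 'Related'. An investigator who applied 'Unrelated' literally and treated everything else as related would err the other way. This also stands: the one-way result holds for use of the 'Related' definition in place of the question, not for every way of handling the gap. A reader might infer that related events will be under-counted. The documents show only that they could be.

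Two further strong readings go beyond the text. One is that 'Related' requires every conceivable alternative to be excluded. The definition names only concurrent disease, other drugs and chemicals, so an infection after exposure to a pathogen, for example, is not plainly ruled out. The other is that SUSARs will be under-reported. Section 8.3.1.4 applies the reasonable-possibility condition, and Section 8.3.1.2.4 lets the Sponsor judge relatedness as well as the investigator. The protection is partial, because Section 8.3.1.2.4 still relies on a judgment of 'related'. Nor does either document say that a Sponsor judgment changes the investigator's flag in the tables.

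**Conclusion.** Table 3 is internally inconsistent, and one foreseeable class of event has no matching definition. That conclusion rests on the wording alone and needs no assumption about rates.

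The consequence is limited to three things: the related-TEAE and related-SAE summaries; causality coding that may differ between sites; and SAEs that arise after both the end of study and 30 days from the last dose. All-cause TEAE and SAE results, which carry the secondary safety objective, are untouched. Follow-up under Protocol Section 8.3.1.5 covers all AEs, with emphasis on related ones, so it does not hinge on the flag.

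No size can be put on the effect, and loss from the related counts is possible, not certain. If loss occurs and is equal across arms, it lowers related-event rates and shrinks absolute differences without reversing them. This is a worthwhile correction of wording, and it does not call the main safety comparison into question.

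**What to change.** Reword Table 3 so that the two categories cover every event and match the question already asked:

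- **Related:** there is a reasonable possibility that study treatment caused the event, even if other causes are possible.
- **Unrelated:** there is no reasonable possibility that study treatment caused the event.

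Keep the list of factors as aids to judgment. Repeat the two definitions in the eCRF completion guidelines mentioned in Protocol Section 11.4.2, with one sentence on events that have plausible timing and another possible cause. This also brings the flag into line with the SUSAR condition in Section 8.3.1.4.

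No visit, test or analysis is added. The costs are a protocol amendment with the approvals in Section 11.2, re-instruction of about 65 sites, and somewhat more events classed as related. If the change is made after enrolment has started, events already coded should be re-assessed under the new wording, while still blinded. Otherwise the related-event tables must state that two standards were used and from what date.

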8.3.1.2.4. Suspected Unexpected Adverse Reactions (SUSARs)

Suspected unexpected adverse reactions (SUSARs) are SAEs that are unexpected per the Reference Safety Information section of the IB and judged by the Investigator and/or Sponsor to be related to ESK-001.

An adverse reaction is ‘unexpected’ if its nature and severity are not consistent with the information about the study drug:

- In the case of a product with a marketing authorization, in the summary of product characteristics for that product.
- In the case of any other investigational product, in the Investigator’s Brochure relating to the trial in question

The Sponsor or designee will report SUSARs to the appropriate regulatory authorities and Investigator’s as required, according to the local law.

8.3.1.3. Reporting Adverse Events

Diagnosis versus Signs and Symptoms

If known, a diagnosis should be recorded on the eCRF rather than individual signs and symptoms (e.g., record only liver failure or hepatitis rather than jaundice, asterixis, and elevated transaminases). However, if a constellation of signs and/or symptoms cannot be medically characterized as a single diagnosis or syndrome at the time of reporting, each individual event

should be recorded as an AE or SAE on the eCRF. If a diagnosis is subsequently established, it should be reported as follow-up information and the diagnosis entered in the eCRF.

AEs Occurring Secondary to Other Events

In general, AEs occurring secondary to other events (e.g., cascade events or clinical sequelae) should be identified by their primary cause. For example, if severe diarrhea is known to have resulted in dehydration, it is sufficient to record only diarrhea as an AE or SAE on the eCRF.

However, medically significant AEs occurring secondary to an initiating event that are separated in time should be recorded as independent events on the eCRF. For example, if a severe gastrointestinal hemorrhage leads to renal failure, both events should be recorded separately on the eCRF.

Persistent or Recurrent AEs

A persistent AE is one that extends continuously, without resolution between subject evaluation time points. Such events should only be recorded once in the eCRF unless their severity changes. If a persistent AE changes in severity, it should be recorded as a separate AE on the Adverse Event eCRF.

A recurrent AE is one that occurs and resolves between subject evaluation time points and subsequently recurs. All recurrent AEs should be recorded on an Adverse Event eCRF.

Abnormal Lab Values

Only clinically significant laboratory abnormalities that require active management will be recorded as AEs or SAEs on the eCRF including but not limited to association with clinical findings, change to study drug (e.g. study drug discontinuation), more frequent follow-up assessments, further diagnostic investigation.

If the clinically significant laboratory abnormality is a sign of a disease or syndrome (e.g., increased alkaline phosphatase associated with cholecystitis), only the diagnosis (e.g., cholecystitis) should be recorded on the eCRF.

If the clinically significant laboratory abnormality is not a sign of a disease or syndrome, the abnormality itself should be recorded as an AE or SAE on the eCRF. If the laboratory abnormality can be characterized by a precise clinical term, the clinical term should be recorded as the AE or SAE. For example, an elevated serum potassium level should be recorded as “hyperkalemia”.

Observations of the same clinically significant laboratory abnormality from visit to visit should not be repeatedly recorded as AEs or SAEs on the Adverse Event eCRF, unless their severity, seriousness, or etiology changes.

Follow up of abnormal lab values: Repeat testing of the abnormal labs should be performed as clinically indicated, in the opinion of the Investigator, until they have returned to the normal range and/or an adequate explanation of the abnormality is found and the lab value stabilizes.

8.3.1.4. Reporting of SAEs

Any AE that is serious and that occurs during the course of the study from the signing of the informed consent to end of study for each patient must be reported by the Investigator to the following:

- The Sponsor (or designee) and study monitor within 24 hours of the Investigator becoming aware of the event (expedited reporting).
- The investigation site's IRB/IEC by the Investigator in accordance with their regulations.

Initial Notification of a Serious Adverse Event (SAE)

Pharmacovigilance must be informed in writing 24 hours from the time the site investigational team first becomes aware of the event using the EDC system, as well as completing a paper SAE report forms.

A paper SAE form including a written, narrative description of any SAE must be sent via email (preferred) or fax within 24 hours after awareness of the event to:

Email: [REDACTED]

Phone: [REDACTED]

Fax: [REDACTED]

Paper SAE forms must be retained in the Investigator Site File.

In addition to reporting the SAE in the EDC and emailing the paper form, the local CRA and the Medical Monitor must be alerted via phone.

As further information regarding the SAE becomes available, follow-up information should be documented as an update using the paper SAE form. Follow-up information should be reported with 24 hours of awareness.

Related SAEs must be collected and reported regardless of the time elapsed from the last administration of study drug, even if the study has been closed.

Unrelated SAEs must be collected and reported during the study and for up to 30 days after the last dose of study medication.

SUSARs are reported to Investigators at each site and associated IRB/IEC when the following conditions occur:

- The event is an SAE
- There is reasonable possibility that the event is an adverse reaction caused by the administered drug
- The adverse reaction is unexpected, that is to say, not foreseen in the IB

Individual SUSARs considered to be a significant safety issues and/or which result in a change to the informed consent form will be reported in an expedited manner to all Investigators and IRB/IECs.

Reporting of any SAEs to applicable regulatory authorities will be the responsibility of the Local Sponsor in compliance with local regulations.

